Grade 3 (AST or ALT > 20 times ULN and/or TB > 3.0-times ULN	-Hold study drug/study regimen dose until	For Grade 3 or 4 AST or ALT and/or TB elevation:  - Promptly initiate empiric IV methylprednisolone at 1 to 4 mg/kg/day or equivalent  - If still no improvement within 3-5 days despite 1 to 4 mg/kg/day methylprednisolone IV or equivalent,	

<sup>4 ASCO Educational Book 2015 "Managing Immune Checkpoint Blocking Antibody Side Effects", by Michael Postow MD.

Immune-Mediated Reactions			ns
		Dose Modifications	Toxicity Management
	Grade 4 (AST or ALT > 20 times ULN and/or TB > 10 times ULN)	baseline within 14 days and after completion with steroid taper.  Permanently discontinue study drug/study regimen if the elevations do not downgrade to ≤ Grade 1 or baseline within 14 days  For elevations in transaminases > 8 × ULN or elevations in bilirubin > 5 × ULN, discontinue study drug/study regimen  Permanently discontinue study drug/study regimen for any case meeting Hy's law criteria (AST and/or ALT > 3x ULN + bilirubin > 2x ULN without initial findings of cholestasis (ie, elevated alkaline P04) and in the absence of any alternative causeiv Permanently discontinue study drug/study regimen	
 
promptly start treatment with immunosuppressive therapy (mycophenolate mofetil) Discuss with study physician if mycophenolate is not available. Infliximab should NOT be used.
 
Hepatology consult, abdominal workup, and imaging as appropriate.
 
Once improving, gradually taper steroids over ≥28 days and consider prophylactic antibiotics, antifungals and anti PCP treatment (please refer to current NCCN guidelines for treatment of cancer-related infections [Category 2B recommendation])
 

Nephritis or Renal Dysfunction (Elevated Serum Creatinine)	Grade of Elevated Serum Creatinine (CTCAE version 4.03)  Any Grade	General Guidance	
 
Consult with Nephrologist
 
Monitor for signs and symptoms that may be related to changes in renal function (eg, routine urinalysis, elevated serum BUN and creatinine, decreased creatinine clearance, electrolyte imbalance, decrease in urine output, proteinuria, etc.)
 
Patients should be thoroughly evaluated to rule out any alternative etiology (eg, disease progression, infections etc.)
 
Steroids should be considered in the absence of clear alternative etiology even for low grade events (Grade 2), in order to prevent potential progression to higher grade event
 

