	Grade 3 or 4 (Grade 3: Serum Creatinine > 3.0 X baseline; >3.0-6.0 X ULN  Grade 4: Serum Creatinine > 6.0 X ULN)	Permanently discontinue study drug/study regimen	
 
Carefully monitor serum creatinine on daily basis
 
Consult Nephrologist and consider renal biopsy if clinically indicated
 
Promptly start prednisone 1 to 2 mg/kg/day PO or IV equivalent
 
If event is not responsive within 3-5 days or worsens despite prednisone at 1-2 mg/kg/day PO or IV equivalent, additional workup should be considered and prompt treatment with IV methylprednisolone 2-4mg/kg/day started.
 
Once improving, gradually taper steroids over ≥28 days and consider prophylactic antibiotics, antifungals and anti PCP treatment (please refer to current NCCN guidelines for treatment of cancer-related infections [Category 2B recommendation]
 

Rash (excluding Bullous skin formations)	Grade of Skin Rash (Please refer to NCI CTCAE version 4.03 for definition of severity/grade depending on type of skin rash) Grade 1	No dose modification	Monitor for signs and symptoms of dermatitis (rash and pruritus)  **IF THERE IS ANY BULLOUS FORMATION, THE STUDY PHYSICIAN SHOULD BE CONTACTED AND STUDY DRUG DISCONTINUED**  For Grade 1:
	Grade 2	For persistent (> 1- 2 weeks) Grade 2 events, hold scheduled study drug/study regimen	
 
Consider symptomatic treatment including oral antipruritics (eg, diphenhydramine or hydroxyzine) and topical therapy (eg, urea cream)
 
For Grade 2:
 
Obtain dermatology consult
 

	Immune-Mediated Reaction	ns
	Dose Modifications	Toxicity Management
	
 
until resolution to ≤ Grade 1 or baseline
 
If toxicity worsens then treat as Grade 3
 
If toxicity improves to ≤ Grade 1 or baseline then resume study drug/study regimen after completion of steroid taper.
 
	
 
Consider symptomatic treatment including oral antiprurities (eg, diphenhydramine or hydroxyzine) and topical therapy (eg, urea cream)
 
Consider moderate-strength topical steroid
 
If no improvement of rash/skin lesions occurs within 3-5 days or is worsening despite symptomatic treatment and/or use of moderate strength topical steroid, discuss with study physician and promptly start systemic steroids prednisone 1-2 mg/kg/day PO or IV equivalent
 
Consider skin biopsy if persistent for >1-2 weeks or recurs
 

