Grade 3	Hold study drug/study regimen until resolution to ≤ Grade 1 or baseline  If temporarily holding the study drug/study regimen does not provide improvement of the Grade 3 skin rash to ≤ Grade 1 or baseline within 30 days, then permanently discontinue Study drug/study regimen	For Grade 3 or 4:  - Consult dermatology  - Promptly initiate empiric IV methylprednisolone 1 to 4 mg/kg/day or equivalent  - Consider hospitalization  - Monitor extent of rash [Rule of Nines]  - Consider skin biopsy (preferably more than 1) as
Grade 4	Permanently discontinue study drug/study regimen	
 
clinically feasible.
 
Once improving, gradually taper steroids over ≥28 days and consider prophylactic antibiotics, antifungals and anti PCP treatment (please refer to current NCCN guidelines for treatment of cancer-related infections [Category 2B recommendation])
 
Discuss with Study Physician
 

		Immune-Mediated Reaction	ons
		Dose Modifications	Toxicity Management
Endocrinopathy (eg, hyperthyroidism, hypothyroidism, hypopituitarism, adrenal insufficiency, etc.)	Any Grade (Depending on the type of endocrinopathy, refer to NCI CTCAE version 4.03 for defining the CTC grade/severity)	General Guidance	
 
Consult Endocrinologist
 
Monitor patients for signs and symptoms of endocrinopathies. Non-specific symptoms include headache, fatigue, behavior changes, changed mental status, vertigo, abdominal pain, unusual bowel habits, hypotension and weakness.
 
Patients should be thoroughly evaluated to rule out any alternative etiology (eg, disease progression including brain metastases, infections, etc.)
 
Monitor and evaluate thyroid function tests: TSH, free T3 and free T4 and other relevant endocrine labs depending on suspected endocrinopathy.
 
If a patient experiences an AE that is thought to be possibly of autoimmune nature (eg, thyroiditis, pancreatitis, hypophysitis, diabetes insipidus), the investigator should send a blood sample for appropriate autoimmune antibody testing
 

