Grade 2	
 
For acute motor neuropathies or neurotoxicity, hold study drug/study regimen dose until resolution to ≤ Grade 1
 
For sensory neuropathy/neuropathic pain, consider holding study drug/study regimen dose until resolution to ≤ Grade 1.         
 
If toxicity worsens then treat as Grade 3 or Grade 4
 
 
 
Study drug/study regimen can be resumed once event improves to ≤ Grade 1 stabilizes after completion of steroid taper
 
	
 
Discuss with the study physician
 
Obtain Neurology Consult
 
Sensory neuropathy/neuropathic pain may be managed by appropriate medications (eg, gabapentin, duloxetine, etc.)
 
Promptly start systemic steroids prednisone 1-2mg/kg/day PO or IV equivalent
 
If no improvement within 3-5 days despite 1-2mg/kg/day prednisone PO or IV equivalent consider additional workup and promptly treat with additional immunosuppressive therapy (eg, IVIG)
 

Grade 3	Hold Study drug/study regimen dose until resolution to ≤ Grade 1	For Grade 3 or 4:  - Discuss with study physician

	Immune-Mediated Reactions								
		Dose Modifications		Toxicity Management					
		• Permanently discontinue Study drug/study regimen if Grade 3 irAE does not resolve to ≤ Grade 1 within 30 days.	- - -	Obtain Neurology Consult Consider hospitalization Promptly initiate empiric IV methylprednisolone 1 to 2 mg/kg/day or equivalent If no improvement within 3-5 days despite IV corticosteroids, consider additional workup and promptly treat with additional					
	Grade 4	Permanently discontinue study drug/study regimen		immunosuppressants (eg, IVIG)  Once stable, gradually taper steroids over ≥28 days					

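### On its literal text, Appendix E-1 lets durvalumab restart mid-taper after Grade 3 rash or Grade 3 immune-mediated neurotoxicity, while a held, steroid-treated Grade 2 event in the same row must wait for the taper to finish

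*Protocol*

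**What the plan says.** All of this is in Protocol Appendix E-1 unless stated otherwise.

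**Rash.** At Grade 3 the instruction is "Hold study drug/study regimen until resolution to ≤ Grade 1 or baseline". DURVA is stopped for good if holding it "does not provide improvement of the Grade 3 skin rash to ≤ Grade 1 or baseline within 30 days". The management column for Grade 3 or 4 says "Promptly initiate empiric IV methylprednisolone 1 to 4 mg/kg/day or equivalent", followed by a taper over at least 28 days once the rash is improving. At Grade 2, when the rash has persisted long enough to be held, the rule is "If toxicity improves to ≤ Grade 1 or baseline then resume study drug/study regimen after completion of steroid taper".

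**Immune-mediated neurotoxicity.** At Grade 3 the site is to "hold study drug/study regimen dose until resolution to ≤ Grade 1", with permanent discontinuation if that is not reached within 30 days. Management is IV methylprednisolone at 1 to 2 mg/kg/day, then "Once stable, gradually taper steroids over ≥28 days". At Grade 2 the cell adds "Study drug/study regimen can be resumed once event improves to ≤ Grade 1 stabilizes after completion of steroid taper".

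**Comparators.** Where Grade 3 hepatitis may be re-dosed, the rule is return to Grade 1 or "baseline within 14 days and after completion with steroid taper". Grade 3/4 endocrinopathy other than hypothyroidism also waits for the taper.

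The SAP does not address re-dosing after immune-related events.

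**The concern.** In these two rows the more severe event has the looser release condition once a hold is in place. A site following the Grade 3 cell as written can give DURVA while the subject is still on daily steroids for that event, before it has been shown to stay at Grade 1 or less without them. Another site may carry the Grade 2 rule upward and wait. Handling would then differ between sites for the events where it matters most.

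The overall-management section of the appendix raises the stakes. Recurrence of a Grade 3 treatment-related event after dosing resumes means permanent discontinuation, and under Section 7.2.4 stopping DURVA for good ends all study treatment. That a mid-taper restart makes recurrence more likely, or that steroids mask an active event, is clinical inference and is not stated in the documents.

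**Working it through.** **Step 1: the cells side by side.**

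| Row and grade | Hold ends at | Time limit | Taper must be complete? |
|---|---|---|---|
| Rash, Grade 2 (held only if it persists beyond 1-2 weeks) | Grade 1 or less, or baseline | none | yes |
| Rash, Grade 3 | Grade 1 or less, or baseline | 30 days | not stated |
| Neurotoxicity, Grade 2 (sensory: holding only to be considered) | Grade 1 or less | none | yes |
| Neurotoxicity, Grade 3 | Grade 1 or less | 30 days | not stated |
| Neuromotor syndromes, Grades 2 and 3 | Grade 1 or less | 30 days | not stated |
| Hepatitis, Grade 3 (where re-dosing is allowed) | Grade 1 or less, or baseline | 14 days | yes |
| Endocrinopathy, Grade 3/4 | symptoms controlled, event stable | none | yes |

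**Step 2: does other text supply the condition?**
- The overall-management row covers toxicities without their own row. Its taper sentence sits under Grade 2, and its Grade 3 entry sends the reader to the specific rows.
- The rule that prednisone must come down to 10 mg/day or less within 12 weeks of the last dose is a stopping rule. It suggests that drug is withheld while steroids fall, but it does not say when dosing may restart.
- Protocol Section 8.2 restricts systemic steroids above 10 mg/day prednisone-equivalent. It governs concomitant medication and sets no restart condition.
- The 30-day limits run on improvement of the event, not on restart. Hepatitis has both a time limit and the taper, so a time limit does not by itself replace the taper.

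No text fills the gap.

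**Step 3: timing.** The plan gives no figure to reproduce. From the documents: taper of at least 28 days, 28-day DURVA cycle. Assumed: day 0 is onset, the taper lasts exactly 28 days and starts on day k = 5 (range 3-7), the event resolves on day R, and the DURVA due date D is uniform over days 0-28. The taper ends on day k + 28, that is day 33 (31-35).

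*(A) Restart at resolution, or on the due date if later.* Section 7.2.4 makes Day 1 of a delayed cycle the day on which treatment resumes. Re-dose day = max(R, D). For R up to 30 this is at most 30, below the earliest taper end of 31, so every case is mid-taper. This follows directly from the assumptions. The gap to taper end, k + 28 − max(R, D), for R = 14 to 30 runs from 31 − 30 = 1 day to 35 − 14 = 21 days.

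*(B) DURVA stays on a fixed 28-day schedule.* The next dose is uniform on R to R + 28. Mid-taper share = (k + 28 − R)/28.

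| R | k = 3 | k = 5 | k = 7 |
|---|---|---|---|
| 14 | 17/28 = 61% | 19/28 = 68% | 21/28 = 75% |
| 21 | 10/28 = 36% | 12/28 = 43% | 14/28 = 50% |
| 30 | 1/28 = 4% | 3/28 = 11% | 5/28 = 18% |

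*Illustrative steroid dose at re-dosing* (assumed 70 kg, linear taper, R = 14, k = 5; Table 7 equates 4 mg methylprednisolone with 5 mg prednisone). Rash: 70 × (1 to 4) × 5/4 × 19/28 = 59 to 238 mg/day prednisone-equivalent. Neurotoxicity: 70 × (1 to 2) × 5/4 × 19/28 = 59 to 119 mg/day.

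**Step 4: what a taper wait would do to DARA.** Section 7.2.4.2 ends DARA after a toxicity delay of more than 28 days. If the first planned DARA dose falls d days after onset (uniform over the dosing interval) and DARA also waited for the taper, the delay would be k + 28 − d, which exceeds 28 when d < k. Share = k/interval: QW 5/7 = 71% (3/7 = 43% to 7/7 = 100%), Q2W 5/14 = 36% (21-50%), Q4W 5/28 = 18% (11-25%).

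**The case against.** The case for leaving the text alone has real content.

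- **A reader might infer that the table never lets a Grade 2 subject receive DURVA on systemic steroids.** The documents do not support that. Grade 2 rash may get prednisone after 3-5 days without improvement but is held only once it has persisted beyond 1-2 weeks. Grade 2 sensory neuropathy is only to be considered for holding. The comparison is therefore limited to Grade 2 events that are actually held and treated with steroids.
- **A reader might infer a drafting error.** That is not proven. Every cell with a 30-day limit omits the taper, including both neuromotor grades, so the omission may be deliberate. Against this, hepatitis pairs a time limit with the taper. The neuromotor row is also a weak precedent, since it calls steroids ineffective as primary treatment for Guillain-Barré.
- **Grade 3 is stricter in other respects.** The hold is unconditional, there is a 30-day stop, both cells call for discussion with the study physician, and recurrence ends treatment. All of this stands. The recurrence rule, however, acts only after the event has come back.
- **The appendix is advisory, and neither Grade 3 cell has a resume sentence.** Both are true. Mid-taper restart is a reading of silence, and Section 8.2 makes an unsupervised restart at high steroid doses less likely. These points lower the weight of the finding, but the two grades still differ.
- **A reader might infer that DURVA must be given steroid-free.** It need not be. DARA pre-medication already puts 60-100 mg methylprednisolone on shared infusion days (Table 6).

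**Conclusion.** The inconsistency holds on the text: both Grade 3 cells release the hold at Grade 1 or less (or baseline, for rash) with no taper condition, and a held Grade 2 event in the same row does not get that release. It is a cheap improvement to advisory guidance. It does not touch the endpoint, sample size or analysis. The shares in the working are conditional on a Grade 3 event that resolves within 30 days and on assumed taper and due dates. The restart rule alone moves the figure from all cases to as few as 4%. How many subjects would be affected cannot be derived from the documents.

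**What to change.** At the next amendment:

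1. In the Grade 3 rash and Grade 3 neurotoxicity cells, add: *DURVA may be resumed after completion of steroid taper.*
2. Keep the 30-day limit and say that it limits time to resolution only, so that waiting for the taper does not trigger it.
3. Apply the same condition to neuromotor Grades 2 and 3 where steroids are used, so that the neurological rows agree.
4. State that the added wait does not apply to DARA and does not count toward the 28-day DARA delay limit in Section 7.2.4.2. Leave the existing DARA hold threshold as it is. Sending DARA to the Grade 2 resumption rule in that section could be looser than the present hold on the study regimen to Grade 1 or less. Say explicitly that DARA may be given while DURVA waits, because Section 7.2.4 covers only the reverse case. Define the taper as the steroid given for the event, since DARA infusions bring their own.

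If re-dosing during the taper is intended, say so in the cell with a maximum daily steroid dose, as the appendix does for endocrinopathies (prednisone 10 mg/day or less).

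The cost is wording in a few cells and a short statement on DARA. With a 28-day taper, DURVA is given about 1-21 days later if dosing can restart at taper end, or one 28-day cycle later in the affected share on a fixed schedule. Longer tapers add to this.

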## Appendix F: Guideline for Asthma Eligibility Criteria

0.000			Classification of Asthma Severity										
Components of Severity					Persistent								
		In	termitte	ent		Mild		N	/lodera	te		Severe	)
		0-4 yrs	5-11 yrs	12 + yrs	0-4 yrs	5-11 yrs	12 + yrs	0-4 yrs	5-11 yrs	12 + yrs	0-4 yrs	5-11 yrs	12 + yrs
	Symptoms	≤	2 days/we	eek	≤ 2 days	s/week but	not daily		Daily		Thro	oughout the	e day
	Nighttime awakenings	0 ≤ 2x/month ≤ 2 days/week		1-2x/ month	3-4x/i	month	3-4x/ > 1x/week but not nightly			> 1x/ month	Often 7	7x/week	
Impairment	SABA use for symptom control (not prevention of EIB)			≤ 2 days/week but not daily more than 1x on any day		Daily		Several time per day		er day			
	Interference with normal activity	None		Minor limitation		So	Some limitation		Extremely limited				
Nomal FEV v /FVC: 8-19 yr 85% 20-39 yr 80% 40-59 yr 75% 60-80 yr 70% FEV 1	· ·	N/A	Normal FEV 1 between exacerbations > 80%	Normal FEV 1 between exacerbations > 80%	N/A	> 80% > 80%	> 80% Normal	N/A	60-80% 75-80%	60-80% Reduced 5%	N/A	< 60% < 75%	< 60% Reduced 5%
Risk	Exacerbations requiring oral systemic corticosteroids	> 85%   Normal		≥ 2 exacerbations in 6 months requiring oral steroids or >4 wheezing episodes/1 year lasting >1 day and risk factors for persistent asthma	≥ 2/year  Relative annual risk may be related to FEV₁.	≥ 2/year Relative annual risk may be related to FEV₁.	≥ 2 exacerbations in 6 months requiring oral steroids or >4 whee zing episodes/1 year lashing >1 day and risk factors for persistent asthma	≥ 2/year  Relative annual risk may be related to FEV₁.	≥ 2/year Relative annual risk may be related to FEV₁.	≥ 2 exacerbations in 6 months requiring oral steroids or >4 wheezing episodes/1 year lasting >1 day and risk factors for persistent asthma	≥ 2/year  Relative annual risk may be related to FEV₁.	≥ 2/year Relative annual risk may be related to FEV₁.	
		Consider severity and interval since last exacerbation. Frequency and severity may fluctuate over time for pat						tients in any s	everity catego	ry. —			
Recommended Step for Initiating Treatment		Step 1				Step 2		Step 3 and consider short course of oral steroids	Step 3: medium dose ICS and consider short course of oral steroids	Step 3 and consider short course of oral steroids	Step 3 and consider short course of oral steroids	Step 3: medium dose ICS OR Step 4 and consider short course of oral steroids	Step 4 or 5 and consider short course of oral steroids
		0-4 y	ears: If no clea	r benefit is obse	erved in 4-6 wee		s, evaluate level ont and consider a				and 12+ years: a	djust therapy ac	cordingly.

## Appendix F: Guideline for Asthma Eligibility Criteria (Continued)

Components of Control		Classification of Asthma Control								
		Well Controlled			Not Well Controlled			Very Poorly Controlled		
		0-4 yrs	5-11 yrs	12 + yrs	0-4 yrs	5-11 yrs	12 + yrs	0-4 yrs	5-11 yrs	12 + yrs
	Symptoms	≤ 2 days/week but not more than once on each day		≤ 2 days/ week	> 2 days/week or multiple times on ≤2 days/week		> 2 days/ week	Throughout the day		
Impairment	Nighttime awakenings	≤ 1x/month		≤ 2x/month	> 1x/month	≥ 2x/month	1-3x/week	> 1x/week	≥ 2x/week	≥ 4x/week
	Interference with normal activity		None		Some limitation			Extremely limited		
	SABA use for symptom control (not prevention of EIB)	≤	2 days/we	ek	> 2 days/week			Several times per day		
	Lung function	N/A			N/A			N/A		
	FEV₁ or peak flow		> 80%	> 80%		60-80%	60-80%	X	< 60%	< 60%
	FEV 1 /FVC		> 80%			75-80%	7.		< 75%	
	Validated questionnaires  ATAQ  ACQ  ACT			0 ≤ 0.75 ≥ 20			1-2 ≥ 1.5 16-19	•		3-4 N/A ≤ 15
	Exacerbations requiring oral systemic	0-1/year			≥ 2/year					
	corticosteroids	Consider severity and interval since last exacerbation								
Risk	Reduction in lung growth/ Progressive loss of lung function			Eva	luation requires long-term follow-up					
Recommended Action for Treatment		Maintain current step     Regular follow-up every 1-6     months     Consider step down if well     controlled for at least 3 months			Step up 1   Step up at step   Step up 1   step   Reevaluate   12-6   weeks   Step up 1   step   Reevaluate   12-6   weeks   Step up 1   step   Step up 1   step up 1			Consider short course of oral steroids Step up 1-2 steps Before step up. Review adherence to medication, inhaler letchnique, and environmental control. If selecting and environmental control or the step of the step of a stimus out of the step of a stimus out of line 2 weeks to achieve control. Of years: If no deer benefit is observed in 4-6 weeks to achieve control. Of years: If no deer benefit is observed in 4-6 weeks, consider alternative diagnoses or 1-5 still years. Adults thereapy accordingly. For side effects, consider alternative treatment opitions		

1. LIST OF ABBREVIATIONS

Table 1: Table of Abbreviations

Abbreviation or Specialist Term	Explanation
ADaM	Analysis data model
AE	Adverse event
AESI	Adverse event of special interest
AUC	Area under the curve
BMI	Body mass index
CIs	Confidence intervals
CL/F	Clearance
Cmax	Maximum observed concentration
CR	Complete response
CRF	Case report/record form
CTCAE	Common Terminology Criteria for Adverse Events
D ²	Daratumumab (DARA) plus durvalumab (DURVA)
DARA	Daratumumab
DURVA	Durvalumab
DMC	Data Monitoring Committee
DNA	Deoxyribonucleic acid
DOR	Duration of response
DRT	Dose Review Team
EBMT	European Group for Blood and Marrow Transplantation
ECG	Electrocardiogram
ECOG	Eastern Cooperative Oncology Group
eCRF	Electronic case report form
EE	Efficacy Evaluable (population)
EOT	End of treatment
FAS	Full analysis set
FDA	Food and Drug Administration
GCP	Good Clinical Practice
ICH	International Council for Harmonisation

IMWG	International Myeloma Working Group
IP	Investigational product
IRAC	Independent Response Adjudication Committee
IV	Intravenous
IVRS	Interactive voice response system
KM	Kaplan-Meier
Max	Maximum
MedDRA	Medical Dictionary for Regulatory Activities
Min	Minimum
MM	Multiple myeloma
CCI	[REDACTED]
NCI	National Cancer Institute
ORR	Overall response rate
OS	Overall survival
PD	Progressive disease
CC I	[REDACTED]
PE	Pulmonary embolism
PFS	Progression-free survival
PK	Pharmacokinetic(s)
PR	Partial response
PS	Performance status
PT	Preferred term
QW	Weekly
Q2W	Every 2 weeks
Q4W	Every 4 weeks
RNA	Ribonucleic acid
RRMM	Relapsed and refractory multiple myeloma
SAP	Statistical analysis plan
SAS	Statistical analysis system
sCR	Stringent complete response
SD	Stable disease
SOC	System organ class
StdDev	Standard Deviation

TEAE	Treatment-emergent adverse event
T_{max}/ t_{max}	Time to peak plasma concentration
$t_{1/2}$	Terminal elimination half-life
TTP	Time to progression
TTR	Time to response
US	United States
VGPR	Very good partial response
VTE	Venous thromboembolism
V_z/F	Volume of distribution
WHO	World health organization

CELGENE PROPRIETARY INFORMATION

